2. TRIAL OBJECTIVE

The primary objective of this study is to prospectively document, using vulvoscopy with detailed photography, the visible changes to the vulva, vestibule and vaginal region in post-menopausal women with dyspareunia taking 60 mg daily ospemifene for twenty weeks at 6 timepoints: baseline, 4 weeks, 8 weeks, 12 weeks, 16 weeks and 20 weeks.

Secondary objectives include changes in pain as noted on the pain scale (appendix 2) and the q-tip test, in the vestibule on visual scale (appendix 3) by the clinician and sexual function by subject diary (appendix 4).

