3. DESCRIPTION OF RESEARCH DESIGN

3.1 Overall Study Plan

This is an unblinded study to be conducted at a single research center, San Diego Sexual Medicine. Subjects meeting inclusion and exclusion criteria will receive 60 mg ospemifene daily for twenty weeks. After the informed consent is

signed, a baseline physical examination, and vulvoscopy with detailed photography of the vulva, vestibule and vagina, will be performed. Physical examination and vulvoscopy with detailed photography of the vulva, vestibule and vagina, will be repeated prospectively every 4 weeks for a total of 20 weeks. Therefore, physical examination and vulvoscopy with detailed photography of the vulva, vestibule and vagina will be performed prospectively at baseline (vulvoscopy session 1), 4 weeks (vulvoscopy session 2), 8 weeks (vulvoscopy session 3), 12, weeks (vulvoscopy session 4), 16 weeks (vulvoscopy session 5) and 20 weeks (vulvoscopy session 6) following daily administration of 60 mg ospemifene.

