4.1 Subject Inclusion Criteria

All criteria below must be met in order for a Subject to be eligible for study participation.

1. Subject provides written informed consent and HIPAA authorization before any study procedures are conducted;

2. Subject is female;
3. Subject is aged 21-80 years;
4. Subject has a body mass index (BMI) < 37 kg/m²
5. Subject is menopausal either naturally (at least 12 months amenorrheic) or 6 weeks after a bilateral salpingo-oophorectomy prior to natural menopause; subjects with hysterectomy only must have a serum FSH > 40 mIU/mL;
6. Subject has vulvovaginal atrophy with dyspareunia;
Subject agrees to comply with the study procedures and visits.

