4.2 Subject Exclusion Criteria

Subjects who meet any of the following criteria shall be excluded:

1. Subject has a hypersensitivity to any of the ingredients of ospemifene;
2. Subject has used ospemifene in the past;
3. Subject has documented or suspected breast cancer, history of heart attack or stroke;
4. Subject has clinically significant findings on physical examination;
5. Subject has uncontrolled hypertension;
6. Subject has any chronic medical condition or psychologic disorder that the Principal Investigator feels makes her ineligible for the study;
7. Subject is currently on local or systemic androgen therapy including local or systemic testosterone (washout 14 days for local or topical androgen or non-depot injection, 1 month for depot, 6 months for pellet);
8. Subject is currently on local or systemic estrogen therapy or androgen therapy (washout 14 days for vaginal estrogen, 60 days for oral/transdermal therapy);
9. Subject is currently using a SERM or products that have estrogenic or anti-estrogenic effects within last month;
10. Subject currently using itraconazole, ketoconazole, digitalis or alkaloids heparin or strong cytochrome P 450 3A4 inhibitors;
11. Subject has a history of substance abuse within 12 months prior, or consuming > 14 alcoholic drinks per week;
12. Subject has received an investigational drug within 30 days prior to signing consent;
13. Subject has any condition or exhibits behavior that indicates to the Principal Investigator that the Subject is unlikely to be compliant with study procedures and visits.

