AN OPEN-LABEL PILOT PROSPECTIVE VULVOSCOPY WITH PHOTOGRAPHY  
STUDY OF THE VISIBLE CHANGES IN THE VULVA, VESTIBULE AND VAGINA PRE-  
AND POST- TWENTY WEEKS OF DAILY ADMINISTRATION OF 60 MG  
OSPEMIFENE IN POST-MENOPAUSAL WOMEN WITH DYSPAREUNIA FROM  
VULVAR VAGINAL ATROPHY

NCT 02784613  
April 4, 2016

Each subject's baseline and end of the study vulvoscopic photographs were subsequently assessed using a four-point rating scale, the vulvoscopic genital tissue appearance (VGTA) scale. The VGTA scale has not been validated. This scale assesses ten different parameters of the appearance of the genital tissue including loss of labia majora, loss of labia minora, decreased size of glans clitoridis, prominence of urethral meatus, stenosis of introitus, vestibular pallor, vestibular erythema, loss of vestibular moisture, loss of vaginal rugae, and loss of prominence of the anterior vaginal wall (Table 2). Each subject could score between 0 and 30 total points on the VGTA at each visit. A higher score of the VGTA scale was considered consistent with a worse vulvoscopic genital tissue appearance.

Baseline physical examination was performed as part of the screening. The physical exam included performance of a cotton-tipped swab testing where the examiner applied gentle pressure at each location of the vestibule: 1:00, 3:00, 5:00, 6:00, 7:00, 9:00, and 11:00 o'clock. The subject was asked to rate her pain on a scale from 0 to 3. Aggregate pain scores at baseline and study end were compared using the Wilcoxon signed-rank test.

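### The swab-test baseline appears to be the screening value, up to 28 days before dosing, although a Day 0 swab is already scheduled; naming Day 0 as baseline is a free improvement

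*SAP*

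**What the plan says.** The swab paragraph of the SAP opens with "Baseline physical examination was performed as part of the screening". It then describes the swab test as part of that examination, with seven vestibular sites each rated 0 to 3, and ends with "Aggregate pain scores at baseline and study end were compared using the Wilcoxon signed-rank test". It does not mention a second pre-dose swab.

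The protocol makes the swab a secondary measure: "Secondary objectives include changes in pain as noted on the pain scale (appendix 2) and the q-tip test" (Section 2). Section 5.2 allows screening up to 28 days before enrolment and lists Q-tip testing there. Section 5.4 lists the same item at Visit 2 (Day 0), the visit at which the first tablets are handed out. Appendix 1 marks the Q-tip test at all seven visits, but the physical examination only at Visits 1 and 7.

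Section 3.1 says that after consent "a baseline physical examination, and vulvoscopy with detailed photography of the vulva, vestibule and vagina, will be performed", without giving a visit number. Section 8.3 classifies pain and visual-scale change against baseline and does not name the visit either.

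**The concern.** The study has one open-label arm. A before/after test there can only attribute change to treatment if the first measurement sits as close as possible to the first dose. If the screening swab is the reference, whatever happens to vestibular tenderness between screening and Day 0 enters the tested difference, and no control group removes it. The length of that untreated stretch also differs from woman to woman.

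A later pre-dose value is already scheduled, and neither document says how it is used. At stake is the interpretation of one secondary comparison, and more generally whether all the before/after summaries start from the same visit.

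**Working it through.** **Which visit is the swab baseline?**

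1. SAP: the baseline examination belongs to screening, the swab belongs to that examination, and the test compares baseline with study end.
2. Appendix 1: before dosing, the physical examination is marked at Visit 1 only. A swab tied to the baseline physical examination is therefore a Visit 1 swab.
3. Section 5.4 and Appendix 1: a second pre-dose Q-tip test exists at Visit 2.

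The screening baseline is thus an inference from adjacent sentences plus the schedule. No single sentence defines it.

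**Which visit is the photographic baseline?** Section 1 and Section 8.1 number baseline as session 0 and count six sessions over the 20 weeks. Appendix 1 schedules seven vulvoscopies. Dropping Visit 1 leaves Visits 2 to 7, which is six sessions at weeks 0, 4, 8, 12, 16 and 20. Session 0 therefore fits Day 0. Section 3.1 does not overturn this. It has the physical examination repeated every 4 weeks, whereas Appendix 1 has it only at Visits 1 and 7, so it uses the term loosely.

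**Length of the baseline-to-end interval (completers).** Inputs: screening-to-Day 0 gap of 0 to 28 days (Sections 5.2, 5.4); final visit at Day 140 ± 7 (Section 5.6).

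- From Day 0: 140 − 7 = 133 to 140 + 7 = 147 days; spread 147 − 133 = 14 days.
- From screening: 133 + 0 = 133 to 147 + 28 = 175 days; spread 175 − 133 = 42 days.
- Untreated share at the nominal maximum: 28 / (140 + 28) = 28/168 = 16.7%.

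These figures measure time, not bias.

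**Illustration of what a drift would do.** The plan states no power, effect size, SD or correlation, so there is no figure to reproduce and every input here is assumed. The simulation used normal scores in SD units, n = 10, the exact two-sided signed-rank test (reject at W ≤ 8, true level 0.0488) and 40,000 replicates. There was no drug effect, and screening scores were higher than Day 0 scores by the stated drift.

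| Drift | Correlation 0.5 | 0.7 | 0.9 |
|---|---|---|---|
| 0.2 SD, screening baseline | 8.4% | 10.9% | 23.5% |
| 0.4 SD, screening baseline | 19.7% | 30.2% | 69.3% |
| Either drift, Day 0 baseline | about 5% | about 5% | about 5% |

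**Power.** With an assumed 0.8 SD effect and equal correlation between visits, either single baseline gives the same power: about 60% at correlation 0.5 and 81% at 0.7. If correlation decays over time, at 0.8 or 0.9 per 28 days, Day 0 gains a little: 44.6% to 48.2%, or 63.0% to 68.5%.

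**Averaging the two pre-dose swabs.** Under equal correlation ρ and unit variance, the variance of change is 2(1 − ρ) with one baseline. With the average it is (1 + ρ)/2 + 1 − 2ρ = 1.5(1 − ρ), which is 25% lower. The average still keeps half of any screening-to-Day 0 drift.

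**The case against.** The strongest reply is that the SAP never says the Visit 1 swab is the analysed value when a Visit 2 swab also exists. On this view the text shows only an unnamed baseline, and the six-session count already points to Day 0 for the photographs, with which the protocol pairs the Q-tip test in one line item. That is fair as to certainty. It does not remove the point, because the only visit the SAP attaches to the swab baseline is screening. If Day 0 was meant, the same sentence is needed to say so.

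Four further replies stand in part:

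- Twenty-eight days is a ceiling, and Day 0 may follow soon after screening.
- The documents give no evidence that swab pain shifts over such a gap. The rejection rates above rest wholly on assumed drifts.
- Averaging is a legitimate alternative if precision matters more than drift. In an uncontrolled study, avoiding drift is the better priority.
- The SAP is in the past tense. If results were already known, switching between two available pre-dose values would be a post hoc choice, free in effort but needing disclosure.

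A reader might also infer that hormone washouts could still be running at the screening swab, because the exclusion criteria do not name the visit from which they count back. The documents do not support building on that. Exclusion item 8 rules out a woman on treatment at the time ("Subject is currently on local or systemic estrogen therapy or androgen therapy"), and Section 5.2 has all criteria reviewed at screening. Section 5.3 bars prescription hormones from screening onward, and the only pre-dose estradiol, LH and FSH are drawn at Visit 1. The text favours washout completed by screening, which leaves no shortfall at the swab.

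**Conclusion.** The point holds as a minor one, and the change is a free improvement. As written, the plan points to a swab baseline up to 28 days before drug, while a better-placed value is already scheduled. The demonstrable consequence is an interval of up to 175 days instead of at most 147, with up to 28 of 168 nominal days (17%) untreated.

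This rests on reading the SAP's adjacent sentences together with Appendix 1, and on treating the Q-tip test at Visits 1 and 2 as the same procedure. The protocol uses identical wording for both visits; the seven-site method appears only in the SAP.

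A reader might go further and conclude that the swab result is biased or that the test is underpowered because of this choice. Neither follows. The direction and size of any drift are unknown, and the gain from Day 0 is protection against bias, with little or no gain in power. The swab is a secondary measure in a 10-woman pilot with no power target.

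**What to change.** State in the SAP and in protocol Sections 8.1 to 8.3 that baseline is the pre-dose Visit 2 (Day 0) value for the swab, pain scale, visual scale and photographs, and that the Visit 1 value is used only if the Visit 2 value is missing. For the photographs this confirms what the session numbering already implies.

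The cost is wording only. Section 5.4 already schedules all four measures at Visit 2, so no visit, test or participant is added. If data had been seen when the change is made, say so and report the screening-baseline swab result beside the Day 0 result as a sensitivity analysis.

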5.2 Subject Screening (Visit 1)

Candidates for enrollment will be screened within 28 days prior to enrollment. Before initiation of any test procedures, Subjects will be fully informed of the study plan, procedures, and risks involved in participating in the study. Each potential Subject will be required to read and to indicate her understanding by signing and dating the ICF prior to initiation of any screening procedures.

The site will maintain an ongoing screening log of all subjects who provide written informed consent. The screening log will include each Subject's initials, date of birth, and screening number (assigned sequentially), including reason for exclusion if the subject is determined to be ineligible for the study. If the subject does not have a middle name, a dash will be used instead of that initial (e.g., J-S). The subject will be identified on source documents by initials and the assigned Subject number.

Screening procedures will consist of the following:

- Medical history, including surgical procedures, tobacco, alcohol, and medication use (prescription and non-prescription drugs, nutritional supplements, herbals, or investigational drugs);
- Measurement of height (inches) and weight (pounds) in indoor clothing without shoes; recorded to the nearest whole unit;
- Vital signs (blood pressure, pulse, respiration rate, and oral temperature);
- Pain scale;
- Urinalysis;
- Clinical laboratory tests estradiol, LH, FSH (the same clinical laboratory will be used throughout the study);
- Physical examination including review of systems and breast and gynecologic exam;
- Vulvoscopy including detailed photograph(s) of the vulva, vestibule and vagina region and pain scale/Q-tip testing;
- Visual scale.

The Principal Investigator will review all screening assessments and sign and date all reports. Any clinically significant abnormalities will be indicated by the abbreviation CS on the report. Results that are not clinically significant will be identified as NCS. The Principal Investigator will review all inclusion and exclusion requirements and document the eligibility of each Subject to participate further.

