5.4 Study Day 0 (Visit 2)

Subject meeting inclusion and exclusion criteria may enroll any time after screening up to 28 days after consent is signed:

- Measure vital signs (blood pressure, pulse, respiration rate, and oral temperature);
- Assess any change in concomitant medication since screening visit;
- Complete pain scale;
- Vulvoscopy including detailed photograph(s) of the vulva, vestibule and vagina region and pain scale/Q-tip testing;
- Complete visual scale;
- Educate subject as to how study medication is administered (taken each morning);
- Dispense study medication (35 tabs), diaries (10) and lubricant;
- Assess adverse events.

5.5 Study Days 28 ± 7, 56 ± 7, 84 ± 7, 112 ± 7 (Visits 3, 4, 5, 6)

Each Subject will report to the Principal Investigator's office on study Days 28, 56, 84 and 112 ± 7 for the following procedures at each visit:

- Measure vital signs (blood pressure, pulse, respiration rate, and oral temperature);
- Assess any change in concomitant medication;
- Complete pain scale;
- Vulvoscopy including photograph(s) of the vulvar vestibule region and pain scale/Q-tip testing;
- Complete visual scale;

- Collect medication and calculate compliance (reeducate Subject on medication administration if compliance is <80% or >120%);
- Collect diaries;
- Dispense study medication (35 tabs), new diaries and new lubricant;
- Assess adverse events.

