8.3 Patient Reported Outcomes

Mean pain score will be summarized at each scheduled visit. Subjects will also be categorized at each visit as having more pain, the same pain, or less pain compared to baseline.

Mean scores will be summarized for each item of the visual scale at each scheduled visit. Subjects will also be categorized at each visit as worsened, unchanged, or improved compared to baseline for each item of the visual scale at each scheduled visit.

For each subject, the proportion of total sexual events with a 'yes' response since the last scheduled visit will be calculated for each diary question at each scheduled visit.

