Baseline sexual function diary data concerning dryness and sexual pain were collected. The questions of the sexual function diary have not been validated. For 4 weeks prior to each study visit, subjects recorded yes or no answers to the following questions for each sexual encounter: 1) did the subject experience dryness before and were you now less dry, 2) did the subject use lubricant during this sexual activity, 3) did the subject experience pain/discomfort during foreplay? 4) did the subject experience pain during masturbation, 5) did the subject experience pain during oral sex, 6) did the subject experience pain during intercourse, and 7) did the subject stop early because of discomfort. Diaries were collected and new ones administered at each subsequent visit. The number of total sexual events, as well as percentage of total sexual events with pain or lubrication difficulty was compared for diaries collected at week 0 and week 20 using the Wilcoxon signed-rank test.

At the completion of the study, the photographs were sorted by subject number and date of exam and assessed by the principal investigator, a sexual medicine physician, who had not examined any of the women in person. He assigned scores to the photographs using pre-determined Likert scales for the 10 parameters of VGTA scale (Table 2). Differences in pre-and post-treatment scores were compared using Wilcoxon signed-rank test for non-parametric matched pairs. All tests of significance were 2-tailed with  $p < 0.05$  considered significant. All analyses were performed in Stata®, version 13.

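### The SAP tests a raw count of sexual events at week 0 against week 20, but the protocol schedules no week-0 diary and does not give the two counts equal recording periods

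*SAP*

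**What the plan says.** The SAP's diary paragraph states: "The number of total sexual events, as well as percentage of total sexual events with pain or lubrication difficulty was compared", and continues "for diaries collected at week 0 and week 20 using the Wilcoxon signed-rank test". The SAP's closing paragraph sets the level: "All tests of significance were 2-tailed with" a 0.05 threshold. Nothing divides the count by days of recording. The paragraph does state a common period: "For 4 weeks prior to each study visit, subjects recorded yes or no answers".

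The protocol differs in four places.

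- **Section 5.2:** "Candidates for enrollment will be screened within 28 days prior to enrollment". Section 5.4 allows enrolment at any time after screening, up to 28 days from consent. Neither section sets a minimum.
- **Section 5.4 (Day 0):** "Dispense study medication (35 tabs), diaries (10) and lubricant". This is the first dispensing of diaries. Section 5.2 and Appendix 1 list none at screening, and neither Section 5.4 nor Appendix 1 lists collection at Day 0. First collection is at Visit 3. Section 5.5 gives no number of forms for later packs.
- **Section 8.3:** the diary analysis is a within-subject proportion of events "since the last scheduled visit will be calculated for each diary question at each scheduled visit". No test of the count is planned there.
- **Appendix 4:** one form is completed per sexual event.

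**The concern.** With unchanged behaviour, the expected count is proportional to the days recorded. A systematic difference in length between the two periods therefore becomes an apparent change in sexual activity. The study has one arm and no control, so nothing else in the design would reveal the artefact. At stake is a statement that women had more sexual events on treatment.

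The more basic problem is that the protocol provides no source for a diary collected at week 0. The period behind one side of the comparison is undefined, so a reader cannot tell whether it was short, was 28 days, or was the first on-treatment month.

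**Working it through.** The plan gives no figure to reproduce: the sample size of 10 rests on a pilot rationale, with no event rate, effect size or power.

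**Week-20 period.** Visit 6 falls on Days 105 to 119 (112 ± 7) and Visit 7 on Days 133 to 147 (140 ± 7).
- Shortest gap: 133 − 119 = 14 days.
- Longest gap: 147 − 105 = 42 days.
- Nominal gap: 140 − 112 = 28 days.

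At a constant 2 events a week these give 4, 12 and 8 events.

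**Week-0 period, two alternative readings.**
- *Reading A, pre-treatment diary.* Consent precedes every study procedure and enrolment is at most 28 days after consent, so the period is at most 28 days. If lengths are spread evenly over 14-28 days the mean is 21, and the expected ratio of counts (week 20 to week 0) is 28/21 = 1.33. Over 7-28 days the mean is 17.5 and the ratio is 28/17.5 = 1.6.
- *Reading B, the pack dispensed at Day 0.* It covers Day 0 to Visit 3 (28 ± 7), which is 21 to 35 days, and holds 10 forms. The cap corresponds to 10/28 × 7 = 2.5 events a week. With Poisson counts, the chance of more than 10 events in 28 days is 0.3% at a mean of 4, 4% at 6, 18% at 8 and 65% at 12.

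**Null simulation.** Each woman's true rate is the same at both times. There are 10 women and 6,000 runs per row, with a two-sided 0.05 signed-rank test (tie-adjusted normal approximation). Assumptions that are not in the documents: Poisson events; rates varying between women (gamma, shape 3); mean 4, 6, 8 or 12 events per 28 days; visit days uniform within ± 7; baseline length uniform over the range shown.

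| Week-0 period | Analysis | Significant increase, mean 4 / 6 / 8 / 12 | Significant decrease |
|---|---|---|---|
| 28 days | raw count | 1.9 / 2.1 / 2.1 / 1.9% | 2.2-2.8% |
| 14-28 days (A) | raw count | 14.9 / 18.2 / 22.6 / 27.1% | 0.2% or less |
| 7-28 days (A) | raw count | 26.9 / 36.0 / 41.5 / 50.2% | 0.0% |
| 21-35 days, first pack capped at 10, final pack uncapped (B) | raw count | 2.8 / 4.7 / 8.4 / 32.2% | 1.6% or less |
| 14-28 days (A) | events per day | 2.2 / 2.6 / 2.8 / 2.4% | 1.8-2.4% |
| 7-28 days (A) | events per day | 2.8 / 2.8 / 2.6 / 3.2% | 1.6-2.3% |

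The nominal rate is 2.5% in each direction. Two further checks mark the limits. A baseline of 21-28 days gives roughly 6-11% significant increases. With 10 forms at both ends, significant increases are no more than about 2.5%, so there is no upward bias.

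**The case against.** The strongest reply is that the SAP already states equal 4-week periods. If they were kept at both ends, the bias disappears; the first row of the table shows this holds even when the final interval ranges over 14-42 days. That stands as a conditional. The protocol does not secure the condition: a pre-treatment diary reaches 28 days only for a woman who waits the maximum time, and no such diary is scheduled.

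Three stronger readings are tempting, and the documents do not support them.

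- *The visit windows favour the drug.* They do not. The 14-42 day spread acts in both directions, and a short final interval looks like less activity. Direction comes only from a week-0 period that is shorter or capped.
- *A short baseline and the 10-form limit both apply.* They belong to mutually exclusive readings. A pack handed out at Day 0 cannot limit a diary kept before Day 0. Reading B also fits poorly with a diary collected at week 0, since that pack comes back at Visit 3.
- *The 10-form limit favours the drug.* This needs later packs to hold more than 10 forms, which is not stated. Even then it matters mainly for women with more than about 2 events a week.

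It is also fair to say that the 28-day limit is an enrolment window, not a documented diary period, and that this is one secondary endpoint in a 10-woman pilot.

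**Conclusion.** The point holds on structure. The SAP tests an unscaled count, the protocol does not guarantee equal recording periods, and its schedule contains no diary that could be collected at week 0. Those statements rest on the documents alone.

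The size is conditional. With a pre-treatment diary of 14-28 days, unchanged behaviour produces a significant increase in about 15-27% of trials, against a nominal 2.5%. The excess shrinks as the baseline approaches 28 days and is absent at 28. With the Day 0 pack as week 0 and larger later packs, the false-increase rate runs from about 3% at 4 events per 28 days to about 32% at 12. Event rates and baseline lengths are assumptions throughout.

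A reader might infer that any reported increase in events is spurious, or that the pain and lubrication percentages share the fault. Neither follows: the actual week-0 period is unknown, and percentages of events are not directly scaled by period length. This should be corrected before the count is interpreted.

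**What to change.** 1. Reconcile the SAP with Sections 5.2 to 5.5 and Appendix 1: state which diary is week 0, when it was dispensed and collected, and the resulting number of days for each woman. If it is the Day 0 to Visit 3 pack, say that this is an on-treatment period.
2. Replace the raw count with events per 28 days observed: dated entries ÷ days from dispensing to collection × 28, compared by the same signed-rank test. In the simulation this brings total false positives to about 4-6%. Counting only the last 28 days before each visit is not a substitute at week 0, because there is no earlier pack to fill a short period.
3. State the number of forms per pack and dispense the same number at every visit, enough for a 42-day interval.

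The cost is a sentence or two in the SAP, additional paper forms, and, if a pre-treatment diary is intended, an entry in the schedule. Appendix 4 already has a date field and visits are dated. If the diaries have already been collected, item 2 is still possible wherever the week-0 dispensing and collection dates exist. Events that went unrecorded for want of forms cannot be recovered, so the number of women who used all 10 should be reported.

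### The SAP tests week-0 against week-20 diaries, but the protocol schedules no diary before study drug is dispensed

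*SAP*

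**What the plan says.** **SAP, diary paragraph.** "Baseline sexual function diary data concerning dryness and sexual pain were collected". On the period covered it says: "For 4 weeks prior to each study visit, subjects recorded yes or no answers". On logistics: "Diaries were collected and new ones administered at each subsequent visit". The count of sexual events and the percentage with pain or lubrication difficulty "was compared for diaries collected at week 0 and week 20 using the Wilcoxon signed-rank test".

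**Protocol.** Section 5.2 introduces the Visit 1 list with "Screening procedures will consist of the following", and no diary appears in that list. At Visit 2 (Section 5.4, Day 0) the step is "Dispense study medication (35 tabs), diaries (10) and lubricant"; Visit 2 has no collection step. Sections 5.5 and 5.6 collect diaries at Visits 3 to 7, and Appendix 1 shows the same pattern. On timing, a woman "may enroll any time after screening up to 28 days after consent is signed".

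Section 2 names sexual function by diary among the secondary objectives. Section 8.3 plans, for each diary question, the proportion of events answered yes since the previous visit. It plans no diary comparison with baseline.

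**The concern.** A paired test needs a value from each woman at both ends. The SAP names week 0 as one end, and the protocol contains no step that produces it. Someone following both documents as written has two options: run no test, or take the first diary collected, which covers the first weeks on drug, and call it baseline.

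This is the only pre/post test planned for the diary objective. A reader of the results could not tell whether a reported change is before versus after treatment or early versus late treatment. These are different quantities, and the second removes whatever drug effect is already present in the first four weeks.

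A true pre-dose diary would raise two further questions. Study lubricant is first supplied on Day 0, so its availability would differ between week 0 and week 20. Diary item 1 (Appendix 4) asks whether the woman is less dry than before, which has no obvious meaning before treatment.

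**Working it through.** The plan gives no figure to reproduce here. The check is a count of scheduled diaries, followed by two short calculations.

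**1. Schedule (Appendix 1, checked against Sections 5.2 and 5.4 to 5.6)**

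| Visit | Day | Drug dispensed | Diaries dispensed | Diaries collected |
|---|---|---|---|---|
| 1 | up to −28 | no | no | no |
| 2 | 0 | yes | yes | no |
| 3 | 28 ± 7 | yes | yes | yes |
| 4 | 56 ± 7 | yes | yes | yes |
| 5 | 84 ± 7 | yes | yes | yes |
| 6 | 112 ± 7 | yes | yes | yes |
| 7 | 140 ± 7 | no | no | yes |

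There are five collections (Visits 3 to 7) and none at week 0. The first diary runs from Day 0 to between Day 28 − 7 = 21 and Day 28 + 7 = 35, all after drug was dispensed. Scheduled week-0 versus week-20 pairs: 0 of 10. The visit text and the table agree, so a broken table does not explain this.

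**2. Coverage of an off-schedule diary kept before Day 0**

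Section 4.1 requires this: "Subject provides written informed consent and HIPAA authorization before any study procedures are conducted". Appendix 1 lists diary dispensing as a procedure. Prospective coverage is therefore at most the number of days from consent to Day 0, which Section 5.4 allows to be anything up to 28.

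- 7 days: 7/28 = 25% of the SAP's 4 weeks
- 14 days: 14/28 = 50%
- 21 days: 21/28 = 75%
- 28 days: 28/28 = 100%

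The stated 4 weeks are possible at week 0 but not assured, and a raw event count from a shorter period is not comparable with one from week 20.

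**3. Using the Day 0 to 28 diary as week 0**

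The documents give no onset time. Purely to show direction, assume that the effect on day t is min(t/T, 1), rising linearly to a plateau at day T, with visits at their nominal days. Let A be the mean effect over Days 0 to 28 and B the mean over Days 112 to 140. The true pre/post change is B − 0 = B, the substitute gives B − A, and the share kept is (B − A)/B.

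| T | A | B | Share kept |
|---|---|---|---|
| immediate | 1.00 | 1.00 | 0% |
| 28 days | 0.50 | 1.00 | 50% |
| 84 days | 14/84 = 0.167 | 1.00 | 83% |
| 140 days | 14/140 = 0.10 | 126/140 = 0.90 | 0.80/0.90 = 89% |

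The loss is greatest with fast onset and smallest with slow build-up. The four values of T are arbitrary, so the table shows direction only and does not estimate the bias in this trial.

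**The case against.** The strongest reply is that the SAP says outright that baseline diary data were collected, in the past tense, and that new diaries were given at each subsequent visit, which implies an earlier one. It also places the baseline physical examination within screening, so a screening-period diary is a plausible reading. That stands. A reader might infer from the schedule that no baseline diary was ever obtained, but the documents do not support this. They show a conflict and an undescribed source.

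A reader might also infer that a 4-week pre-dose diary is possible only if it began on the day of consent and Day 0 fell exactly 28 days later. That is too strict. Four weeks is nominal throughout: with ± 7 day windows, the last on-treatment diary (Visit 6 to Visit 7) could span from 133 − 119 = 14 to 147 − 105 = 42 days, so a pre-dose diary of 21 to 28 days would fit as well as those do. A form completed by recall could reach back before consent, although Appendix 4 asks for completion after each event.

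Nor can it be said that too few pairs would exist to reach significance. The number of week-0 diaries is unknown, and the SAP does not say whether the signed-rank test is exact or uses a normal approximation.

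On item 1, Appendix 4 offers a not-applicable answer, and the SAP does not say which items define lubrication difficulty. It cannot be assumed that item 1 enters the test.

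Finally, this is a secondary objective in a 10-woman pilot, using a diary that the SAP itself describes as not validated. That limits the weight of the point but does not remove the contradiction.

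**Conclusion.** The contradiction holds. The SAP's week-0 versus week-20 diary test has no scheduled week-0 data: five collections, all covering time after drug was dispensed, and 0 of 10 scheduled pairs. Confidence is high in the conflict between the documents; whether a baseline diary was in fact obtained is unknown.

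If one was obtained, its source and actual coverage are not described, 4 full weeks are not assured, and it predates the supply of study lubricant. If the Day 0 to 28 diary is used instead, a pre/post label is wrong. Any true change is understated to the extent that it had begun in the first four weeks, assuming that the effect runs in the same direction in both periods. The size cannot be derived from the documents.

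The point should be fixed before diary results are reported, and it goes no further. The photographs, pain scale and Q-tip test have scheduled baselines, and the by-visit diary proportions in Section 8.3 can be run as planned.

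**What to change.** 1. Reconcile the SAP's diary paragraph with Sections 5.2, 5.4 and 5.5 and Appendix 1. State how and when any week-0 diary was obtained, the period it actually covered, how many women had one, and whether study lubricant was available in that period.
2. If a week-0 diary exists, report event counts per week of actual coverage. Define which diary items make up lubrication difficulty, and either justify what item 1 means at week 0 or leave it out of that comparison. State any difference in lubricant supply as a limitation.
3. If none exists, record that the planned week-0 test could not be done. Label the comparison as first on-treatment period (about week 4) versus week 20, report counts per week of actual coverage, and make no pre/post claim.
4. In either case, keep the by-visit proportions of Section 8.3.

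The cost is SAP wording and reporting only; no visit or procedure changes. The real price is that the pre/post claim for the diary may have to be given up.
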